4.4 Efficacy Analyses

For the analyses of change from baseline of 812P311 efficacy variables (e.g., descriptive statistics), a subject must have both a valid baseline assessment and at least 1 valid post-baseline assessment to be included in the analyses.

Analysis of efficacy will include:

- 1) The Change from baseline (CFB) in the AISRS total score will be summarized using descriptive statistics by visit.
- 2) The CFB in the CGI-S score will be summarized using descriptive statistics by visit.
- 3) The CGI-S will be dichotomized at each visit: CGI-S will be classified as 'responder' if the score is 1 or 2 and 'non-responder' if the score is 3 to 7. The number and percentage of CGI-S responders will be presented by visit.
- 4) The CGI-I will be summarized using descriptive statistics by visit.
- 5) The CGI-I will be dichotomized at each visit: CGI-I will be classified as 'responder' if the score is 1 or 2 and 'non-responder' if the score is 3 to 7. The number and percentage of CGI-I responders will be presented by visit.
- 6) The CFB in the GAD-7 total score will be summarized using descriptive statistics by visit.
- 7) The CFB in the AISRS Inattention subscale score and Hyperactivity/Impulsivity subscale scores will be summarized using descriptive statistics by visit
- 8) The AISRS 50% responder rate: A 50% responder rate is defined as the percentage of subjects with ≥ 50% reduction in AISRS total score from baseline at each visit, where % reduction =100*(AISRS total score - Baseline AISRS total score)/ Baseline AISRS total score.
- 9) The AISRS 30% responder rate: A 30% responder rate is defined as the percentage of subjects with ≥ 30% reduction in AISRS total score from baseline at each visit, where % reduction =100*(AISRS total score - Baseline AISRS total score)/ Baseline AISRS total score.
- 10) The CFB in the Behavior Rating Inventory of Executive Function Adult Version (BRIEF-A) Global Executive Composite (GEC) T-score will be summarized using descriptive statistics by visit.
- 11) The CFB in the BRIEF-A T-score by BRI, MI and their subscales will be summarized using descriptive statistics by visit.
- 12) The CFB in the Symptoms of Depression Questionnaire (SDQ) total score will be summarized using descriptive statistics by visit.
- 13) The CFB in the SDQ subscale scores will be summarized using descriptive statistics by visit.
- 14) The CFB in the Adult ADHD Quality of Life (AAQoL) total score will be summarized using descriptive statistics by visit.
- 15) The CFB in the AAQoL subscale scores will be summarized using descriptive statistics by visit.

Where appropriate, the above endpoints will be summarized descriptively (frequency count and percent) for categorical variables, and number of subjects (n), mean, SD, median, interquartile range (Q1 and Q3), minimum, and maximum for continuous variables.

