#### 2.4. Secondary Efficacy Endpoints

The secondary efficacy endpoints are:

- 1) Change from baseline (CFB) in the AISRS total score by visit.
- 2) CFB in the CGI-S score by visit.
- 3) Percentage of subjects with a CGI-S score of 1 or 2 by visit.
- 4) CGI-I score by visit.
- 5) Percentage of subjects with a CGI-I score of 1 or 2 by visit.
- 6) CFB in the GAD-7 total score by visit.
- 7) CFB in the AISRS Inattention subscale score and Hyperactivity/Impulsivity subscale scores by visit.
- AISRS 50% Responder rate (defined as the percentage of subjects with a ≥ 50% reduction in the CFB AISRS total score) by visit.
- AISRS 30% Responder rate (defined as the percentage of subjects with a ≥ 30% reduction in the CFB AISRS total score) by visit.
- 10) CFB in the BRIEF-A Global Executive Composite (GEC) T-score by visit.
- 11) CFB in the BRIEF-A T-score by each Summary Index Scale and subscale by visit.
- 12) CFB in the SDQ total score by visit.
- 13) CFB in the SDQ subscale scores by visit.
- 14) CFB in the AAQoL total score by visit.
- 15) CFB in the AAQoL subscale scores by visit.

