### 6. STUDY VARIABLES AND ASSESSMENTS

#### 6.1. Efficacy Assessments

#### 6.1.1. Adult ADHD Investigator Symptom Rating Scale (AISRS)

The adult ADHD Investigator Symptom Rating Scale (AISRS) was developed to better measure the presence and severity of ADHD symptoms based on DSM-IV diagnostic criteria in adult patients (**Spencer et al., 2010**). It is a semi-structured clinical interview with suggested prompts for each item to improve interrater reliability. The scale consists of 18 items that directly correspond to the 18 symptoms of ADHD and are further subdivided into two subscales: Inattention (9 items) and Hyperactivity/Impulsivity (9 items). During the interview with the subject, the clinician/investigator rates the frequency and severity of each symptom on a 4-point Likert-type scale, where 0 = None, 1 = Mild, 2 = Moderate, and 3 = Severe, with a maximum total score of 54 points and maximum subscale score of 27 points. The scale allows the assessment of functional impairments linked to each symptom dimension. The AISRS total score is the sum of the Inattention and Hyperactivity/Impulsivity subscale scores.

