2.5 Efficacy Data

 The adult ADHD Investigator Symptom Rating Scale (AISRS) was developed to better measure the presence and severity of ADHD symptoms based on DSM-IV diagnostic criteria in adult subjects⁷. It is a semi-structured clinical interview with suggested prompts for each item to improve inter-rater reliability. The scale consists of 18 items that directly correspond to the 18 symptoms of ADHD and are further subdivided into 2 subscales: Inattention (9 items) and Hyperactivity/Impulsivity (9 items). During the interview with the subject, the clinician/investigator rates the frequency and severity of each symptom on a 4-point Likert-type scale, where 0 = None, 1 = Mild, 2 = Moderate,

Supernus Pharmaceuticals, Inc.

CONFIDENTIAL

and 3 = Severe, with a maximum total score of 54 points and maximum subscale scores of 27 points each.

- 2) The Clinical Global Impressions scale was developed to provide a brief, stand-alone assessment of the clinician's view of a subject's global functioning prior to and after the administration of SPN-812. The Clinical Global Impression Severity of Illness (CGI-S) is a single item clinician rating of clinician's assessment of the severity of the ADHD symptoms in relation to the clinician's total experience with subjects with ADHD. The Clinical Global Impression Improvement Scale (CGI-I) is an assessment of how much the subject's illness has improved or worsened relative to a baseline state prior to treatment. Both CGI-S and CGI-I are rated on a 7-point scale of 1 to 7 with 7 being "extremely ill" or "very much worse", respectively. Successful therapy is indicated by a lower overall score in subsequent testing.
- 3) The CGI-S is evaluated on a 7-point scale with 1 = Normal/not at all ill, 2 = Borderline Ill, 3 = Mildly Ill, 4 = Moderately Ill, 5 = Markedly Ill, 6 = Severely Ill, and 7 = Extremely Ill.
- 4) CGI-I, relative to the condition at baseline, will be evaluated by the investigator at each post-baseline visit on a 7-point scale with 1 = Very much improved, 2 = Much improved, 3 = Minimally improved, 4 = No change, 5 = Minimally worse, 6 = Much worse, and 7 = Very much worse.

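### The AISRS responder formula in the SAP has its sign reversed, so coded as written it counts only subjects who worsened

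*SAP*

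**What the plan says.** SAP section 4.4 defines the two AISRS responder endpoints in words and then by formula. In words, item 8 reads "A 50% responder rate is defined as the percentage of subjects with ≥ 50% reduction in AISRS total score from baseline at each visit" and item 9 reads "A 30% responder rate is defined as the percentage of subjects with ≥ 30% reduction in AISRS total score from baseline at each visit". Each item then adds the same definition: "reduction =100*(AISRS total score - Baseline AISRS total score)/ Baseline AISRS total score".

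The direction of the scale is given in Protocol section 6.1.1: items are scored "where 0 = None, 1 = Mild, 2 = Moderate, and 3 = Severe, with a maximum total score of 54 points". SAP section 2.5 repeats the scoring and the maximum. A fall in the total is therefore an improvement.

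Protocol section 2.4 lists the same two endpoints without a formula, as a reduction of at least 50% or 30%, and describes the quantity as a "reduction in the CFB AISRS total score". The synopsis uses the same wording. Protocol section 7.1 states that the methods in the SAP take precedence over those in the protocol.

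**The concern.** The formula subtracts baseline from the visit score, so an improving subject gets a negative value. The threshold is positive (at least 50, or at least 30). Neither item has a minus sign, an absolute value or a threshold of -50 or -30 that would restore the intended direction.

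If the formula is programmed as it stands, Table 11.11 would show the share of subjects whose AISRS total rose by at least 50% or 30%, under the label of responders. Both items carry the same formula, so comparing one with the other would not expose the error. The protocol supplies no formula to fall back on, and it gives way to the SAP on methods.

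**Working it through.** **Inputs**

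- Rule: responder if % reduction ≥ 50 (item 8) or ≥ 30 (item 9), SAP section 4.4.
- Formula as written: f = 100 × (visit - baseline) / baseline, SAP section 4.4.
- Intended quantity, from the word reduction: g = 100 × (baseline - visit) / baseline = -f.
- Range of the AISRS total: 0 to 54, higher is worse, Protocol section 6.1.1 and SAP section 2.5.

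The documents state no expected responder rate, so there is no figure of the plan's own to reproduce.

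**Step 1. Worked cases**

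| Baseline → visit | f (as written) | Responder as written, 50% / 30% | g (intended) | Responder as intended, 50% / 30% |
|---|---|---|---|---|
| 40 → 20 | 100 × (20 - 40)/40 = -50 | no / no | +50 | yes / yes |
| 40 → 28 | 100 × (28 - 40)/40 = -30 | no / no | +30 | no / yes |
| 40 → 0 | 100 × (0 - 40)/40 = -100 | no / no | +100 | yes / yes |
| 24 → 36 | 100 × (36 - 24)/24 = +50 | yes / yes | -50 | no / no |
| 40 → 52 | 100 × (52 - 40)/40 = +30 | no / yes | -30 | no / no |

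**Step 2. All possible score pairs** (baseline 1 to 54, visit 0 to 54)

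| Threshold | Pairs meeting the rule as written | Pairs meeting the intended rule | Pairs meeting both |
|---|---|---|---|
| 50 | 972, all with visit above baseline | 783, all with visit below baseline | 0 |
| 30 | 1117, all with visit above baseline | 1069, all with visit below baseline | 0 |

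The counts show direction only. They are not expected rates, because real subjects are not spread evenly over the pairs.

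**Step 3. Ceiling**

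Meeting f ≥ 50 requires a visit score of at least 1.5 × baseline. With a maximum of 54, baseline can be at most 54/1.5 = 36. For f ≥ 30 the limit is 54/1.3 = 41.5, so 41 for whole scores. Subjects with higher baselines could never be counted.

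**Step 4. Illustration of size**

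The documents give no AISRS distribution for this population, so the following are assumptions: normal baseline with mean 38 and SD 7, limited to 24 and above; normal change with the mean and SD shown; scores rounded and held within 0 to 54; 400,000 simulated subjects per row. The value 24 is borrowed from the screening score in Inclusion Criteria 'B' (Protocol section 3.3.3.1). Criteria 'A' set no AISRS minimum.

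| Mean change (SD) | Intended rule, 50% / 30% | As written, 50% / 30% |
|---|---|---|
| -18 (11) | 47% / 72% | 0.05% / below 0.5% |
| -8 (10) | 15% / 37% | 0.4% / 2.4% |

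**The case against.** The best defence is that the intent is plain. The verbal definition in each item is correct and unambiguous, and a programmer who follows the words will get the right result. On that view the SAP contradicts itself rather than stating a rule that rewards deterioration. Even if the formula were coded, responder rates near zero beside a mean AISRS fall in Table 11.1 would probably be noticed at output review. The endpoints are secondary and descriptive in a single-arm, open-label safety study, and correct rates can be recovered from the listed AISRS scores. The table shells are in an appendix that is not among the documents, so how Table 11.11 is laid out cannot be checked.

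Much of this stands. The misreport depends on the formula being coded literally. If it were, the table would count only those who worsened by at least 50% or 30%, not everyone who got worse. The simulated rates rest on assumed distributions. The protocol wording is loose, but its direction is still a reduction, so it supports the intended reading and does not share the sign error.

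None of it repairs the formula. The formula is the operational part of the definition, and both programming and its validation may be written to it. An error found only at output review would be corrected after the open-label results had been seen, which is what a pre-specified definition is meant to avoid.

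**Conclusion.** The point holds. In SAP section 4.4, items 8 and 9, the formula contradicts the definition it is meant to make precise. Taken as written with its threshold, it excludes every subject who improves and counts only those who worsen by at least 50% or 30%. That conclusion needs only the formula and the direction of the scale, with no assumption about the data.

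The size of the resulting misstatement does depend on assumptions. In the illustrated cases, true rates of 15% to 72% would appear as 2.4% or less. The damage is confined to two of the 15 efficacy endpoints and Table 11.11. The mean AISRS change (item 1), the safety analyses and the sample size are untouched. It should be corrected before the tables are programmed, because the definition cannot be used as it stands and the correction is certain.

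**What to change.** In SAP section 4.4, items 8 and 9, swap the two scores in the numerator: % reduction = 100 × (baseline total - visit total) / baseline total, with a responder at ≥ 50 (item 8) or ≥ 30 (item 9). An equivalent choice is to keep the present formula, call it percent change, and set the thresholds at ≤ -50 and ≤ -30. Use one form in both items.

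Check the shell and program for Table 11.11 against the corrected definition, using a few known pairs: 40 → 20 must be a responder at both thresholds, 40 → 28 at 30% only, and 24 → 36 at neither.

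As optional tidying at the next amendment, reword the two responder endpoints in the protocol synopsis and section 2.4 so that the reduction refers to the AISRS total score relative to baseline and not to the change score.

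The cost is a one-line edit in each SAP item. Data collection, visits and sample size do not change.

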4.5 Safety Analyses

Safety measures include monitoring, evaluation, and recording of all concomitant medications, and the evaluations of AEs, clinical laboratory test results, vital signs, 12-lead ECGs, C-SSRS, and the performance of physical examinations.

4.5.1 Treatment-emergent Adverse Events

AEs will be coded using MedDRA Version 22.1. All AEs will be considered as treatmentemergent adverse events (TEAEs) and included in the AE summaries.

Adverse events will be categorized by MedDRA SOC and/or PT. A subject experiencing the same AE multiple times will only be counted once for that preferred term. Similarly, if a subject experiences multiple AEs within the same SOC, that subject will be counted only once for that SOC.

For displays, SOCs will be presented in alphabetical order and PTs will be sorted by decreasing incidence under each SOC.

An overview of TEAEs will be provided, this will include summaries of incidence rates (frequencies and percentages) of subjects who had at least one TEAE, serious TEAE, TEAE leading to death, TEAE by maximum severity, TEAE by relationship, TEAE leading to study drug discontinuation, related serious TEAE and Adverse Event of Special Interest (AESI).

TEAEs occurring in at least 5% of subjects will be presented by SOC and PT. TEAEs occurring in at least 5% of subjects by PT will also be presented. In addition, the incidence of TEAEs will also be summarized by MedDRA SOC, PT and maximum severity, in which subjects are counted once for each unique preferred term and each SOC under the known maximum severity at which it was experienced. If severity is unknown for all occurrences of a particular PT, it will be counted under 'severe'. The incidence of TEAEs by MedDRA SOC, PT and relationship to study drug will be produced in the same fashion.

AESIs include seizures or AEs that might represent a seizure (e.g., syncope/syncopal episode, pseudo seizure, myoclonus, severe muscle spasms). To identify the AESI, the following search terms will be used to search among the PTs as well as the verbatim terms: seizure, syncope, syncopal episode, pseudo seizure, myoclonus, and muscle spasms (that is categorized as severe only). The incidence of AESIs will be summarized by MedDRA SOC and PT. For subjects who experienced the same AESI multiple times, the event will be counted once.

4.5.2 Special Safety Categories: Death, Serious Adverse Events and Adverse Events Leading to Study Drug Discontinuation

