#### **Duration of Subject's Participation:**

For subjects who follow **SCHEDULE 'A'**, the total study duration per subject, from Visit 1 to Visit 22/EOS will be up to ~156 weeks (3 years) or until SPN-812 becomes approved and commercially available for Adults.

For subjects who follow **SCHEDULE 'B'**, the total study duration per subject is up to 160 weeks, including screening (up to 4 weeks) and from Visit 1 to Visit 22/EOS (up to ~156 weeks [3 years]), or until SPN-812 becomes approved and commercially available for Adults.

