2 DATA CONVENTIONS FOR ANALYSIS

The Safety Population is defined as all subjects who are enrolled and receive at least one dose of SPN-812 during the OLE study.

Safety will be assessed from data based on the analysis of adverse events (AE), potentially clinically significant (PCS) laboratory evaluations, abnormal liver enzymes and liver function tests, abnormal vital signs, electrocardiogram (ECG) results, Columbia Suicide Severity Rating Scale (C-SSRS) and caffeine intake. Subject disposition (including reasons for premature terminations), subject demographics, physical assessment, and exposure to study drug will also be presented.

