3 STATISTICAL METHODS

3.1 General Methods

Premier Research, the designated CRO, will perform all statistical analysis using SAS version 9.4 or higher. Premier Research will be responsible for creating table, listing, and figure reports by SAS programming and delivering the reports, as well as the programs, to Supernus at study completion.

All analyses will be based on subjects who received any amount of study drug in Study 812P311. This will be referred to as the Safety Population. Since subjects received variable dosing in this study, all subject data will be summarized together under All SPN-812.

For categorical variables, summary statistics will include the number and percentage of subjects within each category (with a category for missing data). Percentages will be based on the total number of subjects with non-missing data. For continuous variables, summary statistics will include the number of non-missing observations, mean, standard deviation (SD), median, and interquartile range (Q1, Q3), minimum, maximum.

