4.3 Study Drug Exposure

Duration of exposure in days will be calculated from the first and last dates of the study drug administration. The duration of exposure will be calculated as date of last dose minus date of first dose + 1. Duration of exposure (days) will be summarized by categories, descriptive statistics, and by age group (18 to 44, 45 to 65, and overall). The categories for duration of exposure are: 0 to <13, 13 to <26, 26 to <39, 39 to < 52, 52 to < 65, 65 to < 78, 78 to < 91, 91 to <104, 104 to < 117, 117 to < 130, 130 to < 144, and 144 or more weeks. The actual average daily dose (0 to ≤ 200 , 200 to ≤ 300 , 300 to ≤ 400 , 400 to ≤ 500 , and > 500 mg/day) will be summarized by duration of exposure categories and by age group. Descriptive statistics for planned dose (n, mean, SD, median, min, max, and Q1, Q3) will be summarized by visit and by age group. The actual average daily dose is calculated as dispensed SPN-812 in mg minus returned SPN-812 in mg divided by days taken SPN-812 across all available visits.

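### Adverse events are summarised only as crude percentages of subjects, although time on drug may run from one dose to beyond three years

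*SAP*

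**What the plan says.** Adverse events head the list of primary safety endpoints (Protocol 2.3), and the primary objective concerns long-term safety (Protocol 2.1).

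- **Measure.** SAP 4.5.1 plans "summaries of incidence rates (frequencies and percentages) of subjects who had at least one TEAE". The same overview covers serious events, events leading to discontinuation and events of special interest.
- **Counting.** "A subject experiencing the same AE multiple times will only be counted once for that preferred term". The same applies within a system organ class.
- **Denominator.** SAP 3.1: "Percentages will be based on the total number of subjects with non-missing data". There is one group: "all subject data will be summarized together under All SPN-812".
- **Shortest exposure.** The Safety Population is everyone "enrolled and receive at least one dose of SPN-812 during the OLE study".
- **Longest exposure.** The synopsis gives a duration "from Visit 1 to Visit 22/EOS will be up to ~156 weeks (3 years) or until SPN-812 becomes approved" and available. Protocol 3.4 lets subjects continue beyond Visit 22 if the drug is not yet approved for adults. SAP 4.3 provides twelve exposure bands, the first below 13 weeks and the last open-ended from 144 weeks.
- **Exposure data.** SAP 4.3: "The duration of exposure will be calculated as date of last dose minus date of first dose + 1". This feeds Tables 3.1 and 3.3, which are separate from the adverse-event tables.
- **Display threshold.** "TEAEs occurring in at least 5% of subjects will be presented by SOC and PT", with a further display by preferred term.

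The titles of Tables 4.1 to 4.8 in SAP 5.1 name no person-year rate, time to first event, cumulative incidence or onset interval. Protocol 7.9 also speaks of an incidence rate without giving a time denominator.

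**The concern.** A subject who took one capsule and a subject treated for three years count equally in the denominator. The result is called a rate but has no unit of time. If events accrue with time on drug, the same underlying risk gives a lower percentage when subjects leave early. Follow-up can end for reasons unrelated to safety, such as commercial availability, so the figure partly reflects the calendar.

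At stake is what a long-term extension is for: whether risk fades, stays level or builds with continued use. Pooled percentages cannot show this. Total person-time can be approximated by hand from Tables 3.1 and 3.3, but time at risk up to the first event of each type cannot.

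**Working it through.** The documents state no expected dropout, event rate, sample-size calculation or power (Protocol 7.10), so there is no planned figure to reproduce. The check asks how far a crude percentage can move when only retention changes.

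**Inputs.** Maximum follow-up T = 3 years (Protocol synopsis). Assumed: a constant hazard λ of first event, and a constant dropout hazard k = −ln(1 − d), where d is the annual dropout proportion.

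**Formulas.**
- Crude proportion = λ/(λ + k) × [1 − exp(−(λ + k)T)]
- Mean exposure = [1 − exp(−kT)]/k

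**Example.** λ = 0.10 and d = 0.20 give k = 0.2231. Crude = 0.10/0.3231 × [1 − exp(−0.9694)] = 0.3095 × 0.6207 = 0.192. Mean exposure = (1 − 0.512)/0.2231 = 2.19 years.

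| Annual dropout | Still on drug at 3 years | Mean exposure | Crude %, λ = 10 per 100 PY | Crude %, λ = 5 per 100 PY |
|---|---|---|---|---|
| 20% | 51% | 2.19 y | 19.2 | 10.2 |
| 40% | 22% | 1.54 y | 13.8 | 7.3 |
| 60% | 6% | 1.02 y | 9.4 | 4.9 |

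Each column holds risk fixed, and the percentage still roughly halves from the first row to the last. Reading across, 10 per 100 patient-years at 60% dropout (9.4%) looks like 5 per 100 patient-years at 20% dropout (10.2%).

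**What person-time does.** Mean time at risk to first event or dropout is [1 − exp(−(λ + k)T)]/(λ + k). For λ = 0.10 this is 1.92 years at 20% dropout and 0.94 years at 60%. Dividing the unrounded crude proportion by it returns 10 per 100 patient-years in both rows.

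**Counter-case: early onset.** Suppose the hazard is confined to the first 28 days and would affect 10% of subjects if none left: h = −ln(0.9)/(28/365.25) = 1.374 per year. At 60% annual dropout, crude = 1.374/(1.374 + 0.916) × [1 − exp(−2.291 × 0.0767)] = 9.7%, against 10.0% with no dropout. Retention hardly matters here. A single overall rate would do worse: the same events over total exposure give 10.0/3.00 = 3.3 per 100 patient-years with no dropout and 9.7/1.02 = about 9.5 at 60%. An overall rate alone is therefore not an adequate remedy.

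**The case against.** The study is descriptive and single-arm, and crude subject percentages are a valid display. SAP 4.5.1 spells out in parentheses what it means by incidence rates, so the calculation is not hidden. That stands: the percentages should remain, and the label is a minor matter.

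Four stronger readings are tempting, and the documents do not support them.

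- **That the figures depend on dropout as much as on risk.** No dropout or event rate is given, and 60% annual dropout is an extreme assumption. Early-onset events are nearly insensitive to retention. Early accrual is plausible: Protocol 1.2.3 reports any-event percentages of 43.4% to 58.0% in active arms over 6 to 8 weeks in the four pediatric Phase 3 studies.
- **That the 5% threshold hides events.** Among the table titles, only Table 4.3 carries the threshold. SAP 4.5.1 also plans events by severity and by relationship without it, and Listing 4.1 covers all events. Nor is it apt to contrast 1.2% at three months with 13.9% at three years for a risk of 5 per 100 patient-years. That compares two uniform follow-up times, whereas this trial will have a mixture.
- **That the results cannot be compared with 812P306 or any other study.** They need care over exposure. A person-year rate would not fully repair the comparison, because rollover subjects are mainly selected completers.
- **That the whole primary safety result is crude.** Hematology, chemistry, vital signs, ECG and C-SSRS have by-visit tables. The point concerns adverse events.

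The table shells in Appendix B are not available, so the exact columns cannot be confirmed; the reading rests on SAP 4.5.1 and the titles.

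**Conclusion.** The point holds for adverse-event summaries. As written, they give one pooled percentage per term over very unequal follow-up, with no view of risk over time. For events that accrue, retention alone can shift the percentage materially: about 19% to 9% at 10 per 100 patient-years, and 10.2% to 4.9% at 5 per 100 patient-years, between 20% and 60% annual dropout. These sizes assume constant hazards, dropout independent of event risk, and a three-year limit; none of the rates comes from the documents. For early-onset events the effect is negligible. The gap weakens interpretation of a primary endpoint in a long-term study but does not invalidate what is planned. It should be closed before the tables are programmed.

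**What to change.** 1. Keep the crude percentages and call them percentages of subjects.
2. Add one table of treatment-emergent events by onset interval, for example 0–12, 12–26, 26–52, 52–104 and over 104 weeks, with subjects at risk in each interval as denominator.
3. Add subjects with a first event per 100 patient-years to Tables 4.1, 4.3 and 4.6 to 4.8. End person-time at the first event or at the end of the period in which events are counted. SAP 4.5.1 treats all recorded events as treatment-emergent, so stopping at the last dose would leave later events without matching time at risk.
4. State the rule for partial start dates. Protocol 7.2 gives one, SAP 3.3 rules out imputation, and Protocol 7.1 lets the SAP prevail. Apply the Protocol 7.2 rule to event start dates and reconcile SAP 3.3 with it.
5. Flag events that start after adjunctive stimulant use begins. Protocol 4.3 allows it after 12 weeks, so later intervals mix monotherapy with combined treatment while the objective concerns monotherapy.

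The cost is programming and extra columns, using dates already collected; trial conduct does not change. The overall rate assumes a constant hazard, and the interval table is the check on that.
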